12.5.3.6 Sensitivity Analyses

In order to test the assumptions underpinning the key secondary endpoint analysis the following sensitivity analysis will be performed.

Time to sustained hospital discharge

- 1) Repeated on the PP to assess the impact of important protocol deviations related to efficacy on this endpoint.
- 2) Repeat of the analysis in Section 12.5.3.2 on the ITT where non-COVID-19 related re-admissions are treated as re-admissions due to COVID-19 in the analysis and missing data will be imputed using multiple imputation as described in Section 10.19.1. The median time to sustained discharge will be estimated for each imputed dataset and the average value across each imputed dataset will be presented.

Oxygen Supplemental Free Days up to Day 29

- 1) Repeated on the PP to assess the impact of important protocol deviations related to efficacy on this endpoint.
- 2) Tipping point analysis for the impact of premature trial discontinuation as described in Section 10.19.3.
- 3) Worst Case imputation as per Section 10.19.4.
- 4) An ANOVA model will be fitted for the number of days oxygen free as a response and actual baseline ordinal scale, region and treatment group as factors in the model. This model will be implemented on the imputed datasets as per Section 10.19.1 with the LS means and SEs from the ANOVA models combined using Rubin's Rule (Rubin, 1987).

Subject free of Respiratory Failure at Day 15

- 1) Repeated on the PP to assess the impact of important protocol deviations related to efficacy on this endpoint.
- 2) Tipping point analysis for the impact of premature trial discontinuation as described in Section 10.19.3.
- 3) Worst Case imputation as per Section 10.19.4.

Subjects discharged and free of supplemental oxygen at day 15

- 1) Repeated on the PP to assess the impact of important protocol deviations related to efficacy on this endpoint.
- 2) Tipping point analysis for the impact of premature trial discontinuation as described in Section 10.19.3.
- 3) Worst Case imputation as per Section 10.19.4.

12.5.3.7 Supplementary Analyses

Additional analyses examining the consistency of the intervention effect for the key secondary endpoints will be performed for the subgroups as per Section 12.5.2.4 using the ITT.

12.5.4 Other Secondary Endpoints

Other secondary endpoints assessing proportion of subjects will be compared using similar logistic regression models as described in Appendix 2 with the treatment effect expressed as a difference in proportions. Difference in proportions by treatment (intervention – placebo) will be estimated and 95% CI will be provided. Death prior to endpoint readout will be handled as worst case, that is subject will be assumed to be in mechanical ventilator need, or to be in oxygen need, or not to have fulfilled an improvement of 1 or 2 units. Subjects in ventilator need at readout will be considered in oxygen need. Unless otherwise specified missing data will not be multiply imputed. These secondary endpoints include:

- 1) Proportion of subjects discharged from hospital and free of supplemental oxygen at Days 8, 22 and 29. Missing data will be imputed as per Section 10.19.1.

- 2) Proportion of hospitalized subjects on non-invasive, invasive mechanical ventilation, ECMO or supplemental oxygen use at Days 8, 15, 22, 29 and 60. Missing data will be imputed as per Section 10.19.1.
- 3) Proportions of subjects in each category of the 8-point ordinal scale at Days 8, 15, 22, 29 and 60. This will be based on the complete case (where deaths are considered in category 8 following date of death). This will be the actual recorded 8-point ordinal scale and not the adjusted scale. This analysis will be descriptive only.
- 4) Proportions of subjects in each category of the adjusted 8-point ordinal scale at Days 8, 15, 22, 29 and 60. This will be based on the average of values from each imputed dataset created per the analysis in Section 10.19.1.
- 5) Proportion of subjects needing intensive care unit stay at Days 8, 15, 22, 29 and 60. Deaths will be considered in ICU following date of death. Only documented ICU stay will be considered. Subjects with no documented ICU stay will be included as 0 days.
- 6) Proportion of subjects on invasive mechanical ventilation or ECMO at Days 8, 15, 22, 29 and 60, and duration of use up to Day 60. Missing data will be imputed as per Section 10.19.1.
- 7) Proportion of subjects free of respiratory failure at Days 8, 22, 29 and 60. This data will be imputed as per Section 10.19.1.

Respiratory failure free days up to Day 60 (refer to Section 10.14) will be analyzed as using a Wilcoxon rank-sum test per the key secondary endpoint oxygen supplemental free days up to Day 29.

All-cause mortality up to Days 8, 15, 22 and 29 will be presented. The proportion dead and censored at these timepoints will be calculated.

Endpoints assessing duration of event will be compared between treatments using the Wilcoxon rank sum test. These endpoints are:

- 1) Duration of hospitalization, including re-hospitalization, up to Day 60 (see Section 10.15).
- 2) Duration of hospitalization up to Day 60 including re-hospitalization for any reason (COVID-19 and non-COVID-19) and missing data will be imputed using multiple imputation (see Section 10.15 and 10.19.1).
- 3) Duration of intensive care unit stay, including re-admission, up to Day 60 (see Section 10.16).
- 4) Duration of invasive mechanical ventilation/ECMO use, up to Day 60 (see Section 10.17).

The change from baseline in $\text{SpO}_2/\text{FiO}_2$ at Day 15 will be compared between treatment groups with analysis of covariance (ANCOVA) models with treatment, baseline disease severity, and region as factors, and baseline $\text{SpO}_2/\text{FiO}_2$ as a covariate. The adjusted mean difference between treatments will be given together with 95% CIs and associated 2-sided p-value. For information on the assignment of values of FiO_2 for use in the calculation of this ratio refer to Section 10.18. Only subjects with baseline and Day 15 data such that this ratio can be calculated will be included in the analysis.

All secondary endpoints will be assessed on the ITT population.

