4.1. Overall Design

This is a randomized, double-blind, placebo-controlled, parallel-group, 2-arm, multicenter trial.

- Subjects hospitalized due to ongoing COVID-19 will be enrolled.
- The trial consists of 3 consecutive periods: a screening period of up to 48 hours, a 2-week IMP treatment period and a follow-up period of up to 7 weeks. Daily visits are required until discharge. Discharged subjects should return to the clinic for the Day 15 visit. Days 8, 22, 29 and 60 visits will be conducted as phone or video visits for all discharged subjects.
- The trial duration for an individual subject will not exceed 9 weeks.
- The trial will enroll a total of maximum 300 randomized subjects, 150 per arm (C21 100 mg b.i.d. or placebo for 14 days) according to a 1:1 randomization.
- Blinding will be performed with a matching placebo.
- Randomization occurs at visit 2 and will be stratified by:
 - Disease severity (based on the ordinal scale score at Day 1).
 - Region.
- An independent DMC will actively monitor data from the trial.

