10.9 Visit Windowing

Subjects are expected to attend daily visits until hospital discharge. Visits will be re-initiated in case of a COVID-19 related hospital re-admission. Subjects who do not discharge will have daily assessments up to Day 29. Subjects who do discharge will have visits Day 8, 15, 22, 29, 60. All subjects will have a follow-up visit at Day 60.

No visit windowing will occur for the 8-point ordinal scale. Daily values for the 8-point ordinal scale will be assigned based on the trial day the assessment occurs i.e. the value recorded on trial day X will be assigned as the value of the ordinal scale at Day X in the analysis. For discharged subjects, information on the oxygen use at home between visits will be entered on the concomitant medication page and the daily 8-point ordinal scale value for discharged subjects will be derived. If a subject has oxygen use on a trial day as per Section 10.10, they will be assigned a value of 2 on the adjusted 8-point ordinal scale (refer to Table 3 in Section 10.8) on the trial days between the oxygen start and end day. If Day 29 occurs on trial day greater than 29, for the analysis purposes a value of Day 29 will be assigned. For Day 60 the value collected at the Day 60 visit will be used in the analysis, even if this did not occur on trial Day 60. All endpoints for the 8-point ordinal scale will summarize Day 8, 15, 22, 29 and were applicable Day 60 time points. If a subject has multiple non-missing ordinal scale assessments on a trial day the assessment that occurred on the scheduled visit per the eCRF will be used in the analysis.

For hospitalized subjects, vital signs, supplemental oxygen use and oxygen saturation will be collected daily. Therefore, no visit windows will be assigned and results in the analysis will be summarized for each trial day up to Day 29. Trial day calculation is defined in Section 10.2. If the trial day an assessment occurs on does not align with the visit trial day in the CRF, the trial day will take precedence in terms of analysis. Laboratory assessments (including CRP and LDH) will be conducted while in hospital but not daily. Analysis visit windows as defined in Table 4 will be used for laboratory assessments. If a subject has multiple assessments in a window, the visit closest to the target day will be selected. For visits that are equally close to the target day, the assessment latest in time will be selected.

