10.18 Data handling for SpO₂ and FiO₂

SpO₂ will be collected on the Oxygen saturation form daily for hospitalized subjects. SpO₂ will be collected twice at a visit and the average of the two assessments will be used as the value in the analysis. If only one assessment is available at a visit this will be the value used in the analysis. Discharged subjects will not have site assessments performed. Day 15 will be the only time point examined for this endpoint.

Subjects on low flow oxygen, high flow device or mechanical ventilation will use the value of FiO₂ as entered on the eCRF by the investigator. Subjects on room air will have a value of 21% for FiO₂ assigned. Subjects on ECMO will not have FiO₂ collected. In this case in the calculation of the SpO₂/FiO₂ ratio the last observation for this ratio prior to the subject moving to ECMO ventilation will be used. If the value of FiO₂ is missing, but information on the type of device and oxygen flow is collected, Appendix 3 will be used to assign a value of FiO₂ to use in the calculation of the SpO₂/FiO₂ ratio.

At a visit a subject may have a SpO₂ reading on an oxygen device and another reading at the same visit on room air. In this case the ratio SpO₂/FiO₂ will be calculated using the on room air value only for SpO₂ and a value of 21% for FiO₂.

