10.19 Missing Data

In general, missing safety data will not be imputed. However, safety assessments in the form of <x (i.e. below the lower limit of quantification) or >x (i.e. above the upper limit of quantification) will be imputed as x in the calculation of summary statistics but displayed as <x or >x in the listings. Missing FiO₂ values will be imputed as per Appendix 3.

In all efficacy analysis subjects who die will always be treated as the worst case following the date of death. For endpoints where multiple imputation will not be implemented, subjects who discontinue the trial early will be assessed in the analysis based on their last known status as discussed in Sections 10.15, 10.16 and 10.17. Other missing data will be imputed using multiple imputation as outlined below.

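### SAP 12.5.4 leaves deaths by Day 15 out of the SpO2/FiO2 comparison, against the SAP's own worst-case rule, and the rules for discharged subjects' Day 15 readings conflict

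*SAP*

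**What the plan says.** **Who is analysed.** SAP 12.5.4 compares the change from baseline to Day 15 in SpO2/FiO2 by ANCOVA and restricts the data: "Only subjects with baseline and Day 15 data such that this ratio can be calculated will be included in the analysis". The section then ends: "All secondary endpoints will be assessed on the ITT population". Protocol 9.3.3 specifies the same ANCOVA and gives no rule for deaths in it.

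**Deaths.** SAP 10.19 has a general rule: "In all efficacy analysis subjects who die will always be treated as the worst case following the date of death". It defines no worst value for a ratio. The multiple imputation in 10.19.1 covers ordinal scale scores, not this ratio.

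**Discharged subjects.** SAP 10.18 says: "Discharged subjects will not have site assessments performed. Day 15 will be the only time point examined for this endpoint". Protocol 4.1 says: "Discharged subjects should return to the clinic for the Day 15 visit", and SAP 8.0 repeats this. The schedule of activities marks oxygen saturation at V16 (Day 15).

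**Timing.** The schedule lets V16 fall one day late. SAP 10.9 assigns oxygen saturation no visit window and, where the actual day differs from the CRF visit day, says "the trial day will take precedence in terms of analysis".

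**The concern.** The set that enters this ANCOVA is defined by something that happens after randomization, namely being alive and measurable at Day 15. If C21 prevents deaths, the patients it saves are likely to be among the sickest survivors. They enter the C21 mean, while their placebo counterparts are deleted. The difference then no longer compares randomized groups, and the likely direction is to understate a benefit.

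The SAP also gives two incompatible instructions on deaths and two on discharged subjects. Programmers following different sections would build different analysis sets for a result reported with an adjusted difference, a confidence interval and a p-value under an ITT label. Unless this is settled before unblinding, the choice could be made with results in view.

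**Working it through.** Neither document gives an effect, SD or power for SpO2/FiO2, so there is no planned figure to reproduce. The first check is therefore of the text.

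**1. Deaths.** Under 12.5.4 a subject dead by Day 15 has no calculable ratio and is excluded. Under 10.19 the same subject must count as worst case. Both cannot be followed. Other endpoints do give death a value: -1 oxygen-free days (12.5.3.3), and ICU or invasive ventilation through Day 60 (10.16, 10.17). Subjects on ECMO keep their last ratio (10.18). SAP 6.1, which lists departures from the protocol, does not mention this endpoint.

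**2. Discharged subjects and Day 16.** There are two readings.
- If the 10.18 sentence governs, discharged subjects have no Day 15 reading at all.
- If the schedule governs, those seen on Day 15 are included, and only those seen on Day 16 lack a Day 15 value.

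Hospitalized subjects have a daily reading either way. So these losses are alternatives and cannot be added. Elsewhere 10.9 does handle late readings: its Table 4 gives laboratory data a Day 13-16 window, and a late Day 29 ordinal score is assigned to Day 29. A clinic visit on Day 16 would thus give a valid Day 15 CRP but no Day 15 ratio.

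**3. Unequal removal of deaths.** From SAP 8.1: 150 per arm, with 10% and 2.5% dead by Day 60, so 150 × 0.10 = 15 and 150 × 0.025 = 3.75 deaths. Assume that a share f of these fall by Day 15 and that saved patients lie 150-250 ratio units below other survivors. Saved patients then make up (f × 0.075)/(1 − f × 0.025) of C21 survivors, and the survivor difference shifts by minus that share times the gap.

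| f | Removed, placebo v C21 | Saved share of C21 survivors | Shift, gap 150 | Shift, gap 250 |
|---|---|---|---|---|
| 0.4 | 6.0 v 1.5 | 0.030/0.990 = 3.0% | −4.5 | −7.6 |
| 0.6 | 9.0 v 2.25 | 0.045/0.985 = 4.6% | −6.9 | −11.4 |
| 0.8 | 12.0 v 3.0 | 0.060/0.980 = 6.1% | −9.2 | −15.3 |

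With an assumed SD of 80-100 and 142 analysed per arm, SE = SD × √(2/142) = 9.5 to 11.9. At f = 0.6 the shift is 6.9/11.9 = 0.6 to 11.4/9.5 = 1.2 standard errors. Using 142 per arm presumes that discharged subjects are analysed.

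**4. Direction by simulation.** All parameters are assumed: 400,000 subjects per arm; ratio = 330 − 90 × severity, limited to 60-476; 3-7% of placebo dead and 50-80% discharged by Day 15; C21 severity lower by 0.3 or 0.64 SD. The 0.64 shift gives C21 deaths of 0.6-1.7%, about 0.20-0.24 of the placebo rate, near the design's 2.5/10 = 0.25.

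| Analysed group | Difference, 0.3 SD | Difference, 0.64 SD |
|---|---|---|
| All, deaths at worst value (60) | 26-28 | 53-57 |
| Survivors | 20-22 | 43-47 |
| Survivors still in hospital | 1-6 | 2-12 |

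Within matched settings, dropping deaths lowers the difference from 25.7 to 22.0 (14%) up to 28.0 to 19.8 (29%) for the smaller shift. For the larger shift it falls from 53.3 to 47.0 (12%) up to 56.9 to 42.7 (25%). The last row shows what a literal reading of 10.18 would do; about 20-70 placebo and 8-55 C21 subjects of 150 would remain.

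**The case against.** Several counter-arguments stand.

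- **Discharged subjects.** A reader might infer that the plan excludes them. The documents do not support that. The inclusion rule in 12.5.4 admits anyone with a calculable ratio, and room air is assigned FiO2 of 21%. The 10.18 sentence describes data collection and resembles schedule footnote 4, where the lack of site assessments follows the Day 8 phone or video visit. SAP 10.10 item 1 itself uses oxygen saturation page records for discharged subjects. This is a contradiction to reconcile, not a planned exclusion.
- **Day 16.** The windowing paragraph in 10.9 opens with hospitalized subjects measured daily. For clinic returns it leaves a gap, and the documents do not say how many visits would fall on Day 16.
- **Magnitude.** Only the sample size and the two mortality rates come from the plan. Death timing, the gap and the SD are assumptions. Without a mortality effect, deaths would leave both arms at similar rates.
- **Remedy.** Giving deaths a rank targets a composite of death and oxygenation. It does not recover the effect in patients who would survive on either arm. SAP 10.19 does not say what the worst ratio is, so any choice is a convention.
- **Consequence.** The endpoint is one of many other secondary endpoints, tested without multiplicity adjustment and outside the hierarchy. Mortality itself is the primary endpoint.

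None of this removes the conflict between 10.19 and 12.5.4, or the missing rule for a Day 16 reading.

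**Conclusion.** The concern holds in a limited form. As written, 12.5.4 removes deaths by Day 15 from an analysis labelled ITT, contrary to 10.19. If C21 lowers mortality as the design assumes, removal is unequal and a benefit is probably understated. Both calculations agree on direction: a shift of about −4.5 to −15 units, or 12-29% attenuation relative to an analysis with deaths at the worst value. These sizes are illustrative and rest on the assumptions listed, so they should not be quoted as the expected bias.

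The conflict over discharged subjects is separate and unresolved in the text. It costs either all their Day 15 readings or only those taken on Day 16, never both. The effect is confined to this one non-key result, so the point merits correction but does not threaten the trial's main conclusion.

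**What to change.** Make three SAP changes before unblinding.

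1. **12.5.4:** apply 10.19 by giving subjects who die by Day 15 the lowest rank in a rank-based ANCOVA with the planned factors and baseline adjustment. Keep the present ANCOVA beside it, labelled as a survivor-only analysis, and report the number excluded by arm.
2. **10.9:** assign V16 oxygen saturation readings taken on Days 15-16 to Day 15 when there is no Day 15 reading.
3. **10.18:** limit the sentence on site assessments to the phone or video visits, so that discharged subjects' Day 15 clinic readings are used, in line with protocol 4.1, SAP 8.0 and the schedule.

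The cost is SAP wording and minor programming, with no new data collection. The downside is that the rank for deaths is a convention and its result is not in ratio units. The retained ANCOVA supplies an estimate in those units.

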12.5.5 Exploratory Endpoint Analyses

The change from baseline in CRP and LDH at Day 15 will be compared between treatment groups using an ANCOVA model. Model for CRP and LDH will be multiplicative. CRP and LDH data for all visits will be log-transformed prior to the analysis and the change from baseline for CRP and LDH at each visit will be expressed as a baseline ratio in the analysis. This baseline ratio ($\log(\text{CRP}/\text{LDH})$ at Day 15/Baseline CRP/LDH) will be compared with ANCOVA models adjusting for treatment, baseline disease severity and region as factors and log-transformed baseline CRP or LDH as a covariate.

No imputation for missing data will be performed for exploratory endpoints. The analysis will be performed on the ITT population. The result will then be back-transformed to the linear scale. The back-transformed

geometric mean for both treatment groups as well as the geometric mean ratio (C21 vs Placebo) will be reported together with the 95% confidence intervals. The 2-sided p-value will be presented.

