9.3.4. Exploratory Endpoint Analysis

The change in CRP and LDH from baseline up to Day 15 will be compared between treatment groups with ANCOVA models adjusting for treatment, baseline disease severity and region as factors and baseline as a covariate. Model for CRP and LDH will be multiplicative, that is data being log-transformed prior to analysis and the result back-transformed to the linear scale.

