10.13 Number of Oxygen Free Days

Subjects will be considered oxygen free on a trial day if they do not have supplemental oxygen usage on that day. Supplemental oxygen usage is defined in Section 10.10 and subjects will be assessed for supplemental oxygen usage on each post treatment day up to trial Day 29 (i.e. from trial Day 2 to Day 29).

The number of oxygen free days for a subject will be the sum of the number of oxygen free days in hospital and number of oxygen free days at home if applicable. These days do not need to be consecutive. Missing data will be imputed as per Section 10.19.1.

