Appendix 5: Endpoint Derivation Details

Endpoint	Calculation	Handling of Death	Handling of Missing Data
All-Cause Mortality (Primary Analysis)	Date of event is the date of death Subjects without event will be censored at the time of completion/study discontinuation	n/a	n/a
All-Cause Mortality (Sensitivity Analysis including Multiple Imputation)	Proportion of deaths is the number of subjects with an ordinal scale value of 8 at Day 60	n/a	Missing data at Day 60 will be imputed.
Time to Sustained hospital discharge (Primary Analysis)	Date of event is the last date of discharge (for initial hospitalization or re-hospitalization for COVID-19 reasons) as recorded on the hospitalization form for subjects. If a subject has the event and subsequently withdraws (for reasons other than death) the subject will be treated as having the event If subject does not have event prior to completion/discontinuation the subject is censored at date of completion/discharge (for reasons other than death)	Subjects are treated as worst case (Day 60 is value used in analysis)	n/a
Time to Sustained hospital discharge (Sensitivity Analysis including Multiple Imputation)	Date of event is the last date of discharge (for initial hospitalization or re-hospitalization for any reason) as recorded on the hospitalization form for subjects with no missing data. For subjects with missing data, such that the event occurs at an imputed visit (≤ 2 ordinal scale occurs after which all subsequent visits stay at ≤ 2), time to sustained discharge will be the relative day of the imputed visit. For subject with Imputed data, if subjects discharges prior to missing data being observed and imputed values indicate the subject stays discharged (≤ 2), the last date of discharge recorded in the hospitalization form will be used For subjects with no event based on imputed and missing data, subjects will be censored at date of completion/Day 60.	Subjects are treated as worst case (Day 60 is value used in analysis)	Missing data will be multiple imputed
Number of days oxygen free up to Day 29	Sum of all ordinal scale values of 1, 3, 4 up to Day 29	Death treated as -1	Missing data will be multiple imputed

[figure not shown]
[figure not shown]

Endpoint	Calculation	Handling of Death	Handling of Missing Data

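### SAP Appendix 5 writes oxygen-free days, third in the testing hierarchy, as a sum of ordinal scores where the SAP body and the protocol count days; the CRP/LDH notation in SAP 12.5.5 also needs correcting

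*SAP*

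**What the plan says.** **Oxygen-free days.** SAP 12.0 lists this endpoint third in the fixed sequence. SAP 12.5.3.3 defines it as a number of days per subject, gives subjects who die before Day 29 the value -1, compares the arms by the Wilcoxon rank-sum test with a Hodges-Lehmann difference, and refers to 10.13 for the derivation. SAP 10.13 says: "The number of oxygen free days for a subject will be the sum of the number of oxygen free days in hospital", to which the oxygen-free days at home are added. It fixes the assessed range, "i.e. from trial Day 2 to Day 29". SAP 10.19.1 step 3 treats an adjusted score of 1, 3 or 4 as a yes/no indicator that a given day is oxygen free. The protocol estimand (Section 3) also counts days. The calculation column of SAP Appendix 5 reads differently: "Sum of all ordinal scale values of 1, 3, 4 up to Day 29".

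**CRP and LDH.** Protocol 9.3.4 describes "data being log-transformed prior to analysis and the result back-transformed to the linear scale". SAP 12.5.5 states "Model for CRP and LDH will be multiplicative", log-transforms the values at all visits, and then says that "the change from baseline for CRP and LDH at each visit will be expressed as a baseline ratio in the analysis". The parenthetical that spells out this ratio puts log(CRP/LDH) before the words "at Day 15/Baseline CRP/LDH) will be compared with ANCOVA models adjusting for treatment". The covariate is log baseline, and the back-transformed "geometric mean for both treatment groups as well as the geometric mean ratio (C21 vs Placebo) will be reported together" with 95% confidence intervals.

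**The concern.** The scores 1, 3 and 4 are category labels. Adding them turns a count of good days into a weighted total in which the worse of the oxygen-free categories earn more. The Appendix 5 row for respiratory failure free days is worded as a sum of days, so the oxygen row is out of line with the row type it should match. It also omits the word adjusted. On the unadjusted scale, a discharged subject scored 2 for activity limitation but not on oxygen would earn nothing, contrary to the re-mapping in SAP 10.8.

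A table of derivations is a natural source for programming, and this endpoint can carry a confirmatory claim if the two tests above it succeed. A rank test on the wrong variable can change direction, not only lose power.

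The CRP/LDH point has less at stake. The endpoints are exploratory and outside the hierarchy. But a response with baseline outside the log does not back-transform to the ratio that the section promises.

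**Working it through.** The plan gives no figure to reproduce here. The check applies each rule as written and as defined elsewhere.

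**Oxygen-free days.** Inputs: Days 2 to 29 (SAP 10.13), so 29 - 2 + 1 = 28 days; qualifying scores 1, 3 and 4 (SAP 10.19.1 step 3 and Appendix 5).

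- Count rule: number of days with a qualifying score.
- Literal rule: sum of the scores on those days.

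| Course over the 28 days | Count | Literal sum |
|---|---|---|
| 4 days at 5, then 24 at 1 | 24 | 24 x 1 = 24 |
| 18 days at 5, then 10 at 4 | 10 | 10 x 4 = 40 |
| 7 days at 5, then 21 at 1 | 21 | 21 x 1 = 21 |
| 7 days at 5, 7 at 4, 14 at 1 | 21 | 7 x 4 + 14 x 1 = 42 |
| 28 days at 4 (algebraic ceiling) | 28 | 28 x 4 = 112 |

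Rows 1 and 2 reverse in rank. Rows 3 and 4 have the same number of oxygen-free days, but the subject who stays in hospital a week longer gets twice the total. Seven days at score 4 (7 x 4 = 28) already equal the whole window spent at home at score 1.

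An illustrative simulation shows what this can do to the rank test. All inputs are assumed: 5,000 subjects per arm; Poisson days on oxygen with mean 6 (active) and 7 (placebo); then Poisson hospital days at score 4 with mean 2 and 4; the remaining days at home at score 1; no deaths or missing data.

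- Count: medians 22 and 21, P(active > placebo) = 0.61.
- Literal sum: medians 28 and 33, P(active > placebo) = 0.27.

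The active arm is better on both oxygen and length of stay, yet the literal rule favours placebo.

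**CRP/LDH.** Let X0 and X15 be the baseline and Day 15 values of one analyte. SAP 10.1 defines change as the post-baseline value minus the baseline value. Applied to log-transformed data this is log(X15) - log(X0) = log(X15/X0), and exponentiating a treatment difference on that scale gives a ratio of geometric means, as 12.5.5 intends. The parenthetical as it appears is log(X15)/X0.

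Illustration with assumed values X0 = 100 and X15 = 10 mg/L and natural logs:

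- Log ratio: ln(10/100) = -2.303, which back-transforms to 0.10.
- As written: ln(10)/100 = 0.023, which back-transforms to 1.023.
- If both values are taken as already logged: ln(10)/ln(100) = 0.5, which is not a log ratio either.

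**The case against.** The strongest reply is that nobody following the SAP as a whole would make either mistake.

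For oxygen-free days, the Appendix 5 row is itself titled as a number of days. The operative sections (10.13, 10.19.1 step 3, 12.5.3.3) and the tipping-point rule in 10.19.3 all work with days, and Appendix 5 is described in the change history as a summary. The phrase can even be read charitably as the total number of values equal to 1, 3 or 4. The ceiling of 112 needs score 4 on every day from Day 2 in subjects who enter at score 5 or 6, which is clinically remote. All of this stands, and it limits the consequence. It does not make the row correct, and I found no statement of whether the body or the appendix prevails.

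For CRP/LDH, the parenthetical is shorthand for two analytes, in which one slash plainly means or. The position of the bracket may also have moved in conversion from PDF. That stands too, and is why this is only a notation point.

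Three stronger inferences are tempting, and the documents do not support them:

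- That the SAP contains no usable CRP/LDH formula. SAP 10.1 applied to the logged data supplies one.
- That the reported CRP/LDH ratio would vary between SI and US units. SAP 12.6.3, where both systems are planned, covers descriptive safety summaries and not this ANCOVA.
- That the CRP illustration measures a real error. Its values are assumed, and this trial has no CRP entry criterion.

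**Conclusion.** The Appendix 5 rule for a key secondary endpoint is wrong as written and contradicts the SAP body and the protocol. If it were programmed literally, hospital days at score 3 or 4 would count three or four times a home day at score 1, and the Wilcoxon comparison could reverse. The weighting and the 40 versus 24 example are exact arithmetic. The simulated reversal depends on assumed inputs and shows only that a change of direction is possible.

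A reader might infer that the rank 3 test will be run on the wrong variable. The documents do not show that, because the intended day count is recoverable from several sections. The defect is an inconsistency in a derivation rule: minor in effort, but worth correcting because the endpoint is confirmatory.

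The 12.5.5 notation is secondary. The intended response is log(Day 15) minus log(baseline), and the text should say so.

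**What to change.** - **Appendix 5, oxygen-free days:** replace the calculation with a count, namely the number of days from Day 2 to Day 29 with an adjusted ordinal scale value of 1, 3 or 4 (death = -1). This uses the 10.13 range. Starting at Day 2 loses nothing, since subjects are at score 5 or 6 on Day 1.
- **Program check:** confirm that the analysis program counts days and uses the adjusted scale.
- **SAP 12.5.5:** state the response as log(Day 15 value) minus log(baseline value), separately for CRP and LDH, with log(baseline) as covariate and the treatment difference exponentiated to the geometric mean ratio.

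The cost is two short text edits and one program check before database lock. If lock has passed, record the same clarification and the result of the check. No intended analysis changes.
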